8.7.2 Clinical Criteria for Progression and Active Treatment

The primary outcome of interest in this prevention trial is disease progression defined by (a) PSA doubling time (PSADT) less than 3 years, (b) PSA above 10 at any time, or (c) Gleason score on repeat biopsy ≥ 7 for men younger than 70 years and $\geq 4+3 = 7$ for men 70 years or older. These criteria are drawn from one of the largest active surveillance studies to date, the Toronto cohort (12).

Participants who do not meet PSA or biopsy criteria for progression are strongly encouraged to remain on AS while in the study and not undergo treatment with surgery, radiation, local ablation, or androgen deprivation. These criteria reflect the current standard of care (11,12) and are as follows:

a) PSA doubling time (PSADT) < 3 years

b) PSA ≥ 10 ng/mL

If the treating physician suspects that a single measurement of PSA ≥ 10 ng/mL represents a spurious rise unrelated to cancer progression (e.g., clinical prostatitis, asymptomatic prostatitis in association with a viral syndrome, or instrumentation of the urinary/gastrointestinal tracts), a repeat PSA may be drawn up to 2 weeks later. If the repeat PSA value is less than 10 ng/mL, then that repeat PSA value shall be recorded for that visit. If the repeat PSA value ≥ 10 ng/mL, the first PSA value should be recorded for that visit.

c) Repeat biopsy

- $\geq 25\%$ of biopsy tissue cores positive for cancer
- $> 50\%$ of any one biopsy tissue core positive for cancer
- Men < 70 years at baseline: Gleason sum ≥ 7
- Men ≥ 70 years at baseline: Gleason sum $\geq 4+3 = 7$

It is recognized that some participants will elect to pursue treatment during the study despite not meeting these criteria for progression. These participants will be censored at the time they begin treatment.

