10.4 Analysis of diagnostic prostate biopsy sections (Substudy 151105)

10.4.1 Background

A great deal of information is contained in the prostate tissue in the diagnostic biopsy: the Gleason score, which indicates the aggressiveness of the cancer, and the size and location of the cancer. Higher Gleason score and larger tumor are associated with disease progression. The biopsy tissue can be used to describe the rates at which prostate cells are proliferating and at which prostate cells are undergoing apoptosis. Together, these factors provide an indicator of overall tumor growth index, which is associated with disease progression. The biopsy also can be used to describe the degree to which androgen-signaling proteins, including the androgen receptor, and androgen metabolism enzymes, including 5-alpha reductase 1, 2, and 3, are expressed. Androgen-signaling proteins have been linked to prostate cancer risk and to treatment outcome, with androgen signaling generally associated with the presence or development of more aggressive disease (108-110). Recent advances make possible the detection of small noncoding segments of RNA, known as microRNA, which can be extracted from serum and from tissue fragments. MicroRNAs 141 and 375, which have received a great deal of attention as likely predictors of prostate cancer treatment outcome, will be examined in this study (111, 112). These two microRNAs have been associated with more aggressive disease and with tumor progression.

Taking these key indicators into account in analyses may enable better description of the likelihood that the prostate will respond to dietary change. Although randomized assignment should greatly lessen the likelihood of confounding of outcome by such

baseline characteristics as tumor growth, proteins predictive of outcome, or microRNA; taking these characteristics into account may increase the power of these analyses. In addition, it is possible that these factors may interact with treatment assignment to affect cancer progression.

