10.4.4 Statistical considerations

The baseline biomarkers will be associated with progression-free survival (PFS), time to progression as defined for the main study or death. Specific statistical analysis plans are as follows for each study objective. About 80% of the patients in the main study will participate in this correlative study. With $n = 334 (=418 \times 0.8)$ patients, a Cox regression model to regress PFS on a continuous biomarker will have 95% of power to detect a log-hazard ratio (or, regression coefficient of the Cox proportional hazards model) of 0.4 between two patient groups whose biomarker values are 1 standard deviation away with a two-sided alpha level of 5%. This power calculation is based on 85% of 2-year PFS for the whole population, the accrual and follow-up periods assumed for the main study and the assumption that each marker is normally distributed (possibly after a transformation).

- 10.4.4.1 To compare proliferation, apoptosis and the tumor growth index to dietary intervention assignment as predictors of cancer progression in AS patients**

PFS will be regressed on each biomarker of proliferation (KI-67), apoptosis (cleaved caspase 3) and tumor growth rate (a composite of proliferation and apoptosis) using a Cox regression model. In order to see which biomarkers are independently prognostic, we will also perform a Cox regression to regress PFS on all three of the biomarkers. We will repeat these regression analyses adjusting for treatment allocation to investigate if the effect of these biomarkers is confounded with treatment allocation.

10.4.4.2 To compare proliferation, apoptosis and tumor growth index to outcome predictors among AS patients randomized to dietary intervention as opposed to those assigned to the comparison group

The analyses adjusting for treatment allocation as described in in Section 10.4.4.1 will be repeated by adding the interaction term between each marker and treatment allocation to the regression models to see if the effect of each biomarker is different between the two treatment arms. If any of these interaction terms are significant, then we will also fit a regression model within each arm to develop a prediction model based on the biomarkers for each treatment arm.

10.4.4.3 To compare protein levels of the androgen receptor and 5-alpha reductase 1, 2, and 3 to dietary intervention assignment as predictors of cancer progression in AS patients

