PFS will be regressed on each biomarker of androgen receptor, 5 alpha reductase 1, 5 alpha reductase 2, and 5 alpha reductase 3 using a Cox regression model. In order to see which of these protein level biomarkers are independently prognostic, we will also perform a Cox regression to regress PFS on all four of these biomarkers. We will repeat these regression analyses adjusting for treatment allocation to investigate if the effect of the biomarkers is confounded with treatment allocation.

10.4.4.4 To compare protein levels of the androgen receptor and 5-alpha reductase 1, 2, and 3 as outcome predictors among AS patients randomized to dietary intervention as opposed to those assigned to the comparison group

The analyses adjusting for treatment allocation as described in in Section 10.4.4.3 will be repeated by adding the interaction term between each marker and treatment allocation to the regression models to see if the effect of each biomarker is different between the two treatment arms. If any interaction terms are significant, then we will fit a regression model within each arm to develop a prediction model based on the biomarkers for each treatment arm.

10.4.4.5 To compare expression of microRNAs 141 and 375 to dietary intervention assignment as predictors of cancer progression in AS patients

PFS will be regressed on each biomarker of microRNAs 141 and 375 using a Cox regression model. In order to see which of these microRNAs are independently prognostic, we will also perform a Cox regression to regress PFS on both of the microRNAs. We will repeat these regression analyses adjusting for treatment allocation to investigate if the effect of these biomarkers is confounded with treatment allocation.

The microRNA package we are going to use will examine many more (~200) microRNA biomarkers. We will develop a prediction model for PFS using all the examined microRNA biomarkers as candidate predictors using the gradient lasso procedure,¹¹³ and compare the prediction power of this model with that based on microRNAs 141 and 375. A Cox regression will be conducted including the risk score fitted using the gradient lasso method and treatment allocation.

10.4.4.6 To compare expression of microRNAs 141 and 375 as outcome predictors among AS patients randomized to dietary intervention as opposed to those assigned to the comparison group

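### The marker models in Section 10.4.4 leave out baseline PSA and other clinical predictors, so they can show only that a marker is independent of the other markers in its set

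*Combined protocol and SAP*

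**What the plan says.** Section 10.4.4 relates baseline tissue and microRNA markers to progression-free survival, defined as main-study progression or death. For proliferation, apoptosis and tumour growth, Section 10.4.4.1 fits each marker alone and then all three together: "In order to see which biomarkers are independently prognostic, we will also perform a Cox regression". Section 10.4.4.3 does this for the androgen receptor and three 5-alpha reductases, with the four proteins in one joint model ("In order to see which of these protein level biomarkers are independently prognostic, we will also perform a Cox regression"), and Section 10.4.4.5 for microRNAs 141 and 375. Each set is then refitted with arm: "We will repeat these regression analyses adjusting for treatment allocation to investigate if the effect of the biomarkers is confounded with treatment allocation". Sections 10.4.4.2, 10.4.4.4 and 10.4.4.6 add marker-by-arm interactions. No model in these six subsections names baseline PSA, Gleason score, tumour extent or a stratification factor.

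Other parts of the document treat clinical predictors differently. Section 10.4.1 says: "Higher Gleason score and larger tumor are associated with disease progression". Section 11.3 adjusts the multivariable progression analysis for stratification and other prognostic factors, and adjusts its carotenoid regressions (on PSA doubling time and on time to pathological progression) for intervention and known predictors.

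**The concern.** A reader of the substudy report will take *independently prognostic* to mean that the marker adds to what the clinic already knows. These models cannot show that.

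The planned confounding check is aimed at the wrong variable. Arm is assigned at random, so apart from chance it is unrelated to a marker measured at baseline. The variables that could produce a spurious marker effect are those linked both to the marker and to progression, and none of them is in the model.

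Baseline PSA matters most because one route to an event is defined by the PSA level. A marker that merely tracks baseline PSA could be credited with value of its own and carried into the arm-specific prediction models that follow.

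**Working it through.** **1. What the models contain**

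| Section | Joint model | Added in the repeat |
|---|---|---|
| 10.4.4.1 | 3 tumour-growth markers | arm |
| 10.4.4.3 | 4 protein markers | arm |
| 10.4.4.5 | 2 microRNAs | arm |
| 11.3, time to progression | (arm comparison) | stratification and other prognostic factors |
| 11.3, carotenoid regressions | carotenoids | arm, known predictors, stratification factors |

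**2. The plan's power figure**

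Inputs from Section 10.4.4: n = 334, two-sided 5%, log-HR 0.4 per SD, 2-year PFS 85%. The plan states "95% of power to detect a log-hazard ratio" of that size. The formula is power = Φ(0.4√D − 1.96), where D is the number of events.

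- Three years of accrual with everyone followed to year 5: λ = −ln(0.85)/2. The event probability is 1 − (e^(−2λ) − e^(−5λ))/(3λ) = 24.6%, so D = 82 and power = 95.2%. This reproduces the stated figure.
- 24 months per patient, as Sections 11.1 and 11.2 state: D = 334 × 0.15 = 50 and power = 80.8%.

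The rest uses D of about 50, which matches the stated follow-up. Reconciling the power statement with that follow-up is a separate point.

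**3. How baseline PSA is tied to the endpoint**

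Entry requires PSA below 10 (Section 4.1.11). PSA of 10 or more is an event in Section 11.2; the opening of Section 8.7.2 words it as "PSA above 10 at any time", a difference that does not matter here. Under steady exponential growth from baseline b, the doubling time that just reaches 10 at 24 months is 2 ln 2 / ln(10/b):

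- b = 9: an 11% rise, doubling time 13.2 years.
- b = 3: a 233% rise, doubling time 1.2 years.

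The second man already meets the criterion of a doubling time under 3 years. The two criteria meet where 10/b = 2^(2/3), that is b = 10/1.587 = 6.3. Under this simplification the PSA level adds events beyond the doubling-time criterion only for men entering between about 6.3 and 10.

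**4. How large a spurious effect could be**

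Simple approximation, with assumed inputs: marker-PSA correlation 0.3 and HR 2 per SD of log PSA for the whole endpoint. The apparent log-HR is 0.3 × ln 2 = 0.21, about half of the 0.4 used for sizing. With 50 events, z = 0.21 × √50 ≈ 1.5, and the marker reaches two-sided p < 0.05 in about 31% of trials.

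Simulation, 1,000 runs per cell, n = 334, 45 to 50 events, follow-up 2 years. The marker has no effect of its own. The hazard is λ[(1 − s) + s·exp(x − ½)], where x is standardised baseline PSA (assumed log-HR 1.0 per SD) and s is the PSA-driven share. Percentage significant without adjustment:

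| Share s | correlation 0.2 | 0.3 | 0.5 |
|---|---|---|---|
| 10% | 6 | 6 | 8 |
| 30% | 8 | 9 | 17 |
| 50% | 10 | 16 | 39 |
| 100% | 22 | 46 | 88 |

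Adjusted for baseline PSA, the rate was 5% to 6% in every cell. The share, the correlation and the log-HR are all assumptions; the documents supply none of them.

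**5. What adjustment costs in power**

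Replace D by D(1 − r²), with r the assumed correlation of the marker with the added covariate. At D = 50, power falls from 81% to 77% (r = 0.3) or 69% (r = 0.5). At D = 82 it falls from 95% to 93% or 88%.

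**The case against.** The best defence is that the phrase introduces a joint model of the markers in one set, so its natural meaning is independent of each other. The objectives in Section 10.4.2 compare markers with diet assignment and between arms; none promises value beyond PSA or grade. That is a fair reading, but the plan never states it, and the label will be read more broadly.

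Eligibility also narrows the omitted variables. Gleason 7 (3+4) is allowed only above age 70, about 30% of men, or roughly 100 of 334. Tumour extent is capped at under 25% of cores positive and at most 50% of any one core. This stands: PSA is the stronger case, and grade may add little once age is in the model.

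Overfitting is a real limit. Four markers, arm, log PSA and three binary stratification factors make 9 parameters on about 50 events, or 5 to 6 events each.

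A reader might infer something stronger: that baseline PSA largely determines the PSA-level event, so that any marker correlated with PSA will look independently prognostic. The documents do not support this. Section 11.2 attributes 14% progression to doubling time and 8% to 10% to Gleason, within about 20% overall, and gives no share for the PSA level. Doubling time is a slope, which its definition does not tie to the starting level. At PSA-driven shares of 10% to 30%, the simulated false-positive rate is 6% to 17%. It reaches 88% only if the whole hazard depends on baseline PSA and the correlation is 0.5. Nor does the contrast between entry at 3 and at 9 measure the problem, since the man at 3 is an event by doubling time anyway.

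**Conclusion.** The point holds as a limit on what may be concluded. As written, Sections 10.4.4.1, 10.4.4.3 and 10.4.4.5 can establish independence only from the other markers in the set. A marker that tracks baseline PSA can appear prognostic without an effect of its own. How often depends on quantities that the documents do not give, so the inflation may be negligible or severe. The finding that rests least on those assumptions is that adjustment for baseline PSA held the error rate near 5% in every scenario tried. The threshold of about 6.3 assumes steady exponential growth over 24 months.

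The omission is also out of line with Section 10.4.1 and with the adjustment in Section 11.3. It deserves correction before the substudy is analysed, but it concerns secondary correlative analyses and leaves the primary comparison of arms untouched.

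**What to change.** In Sections 10.4.4.1, 10.4.4.3 and 10.4.4.5:

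- Add a model with log baseline PSA and the stratification factors (age, race, timing of the baseline biopsy), in line with Section 11.3. Add baseline Gleason or tumour extent where they vary enough to be estimated.
- Reserve *independently prognostic* for markers that remain after this adjustment. Otherwise report the marker as independent of the other markers in the set.
- Drop the rationale that adjusting for arm tests confounding. Arm may stay in the model for other reasons, such as the interaction analyses.

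The cost is SAP wording. Baseline PSA, biopsy material and the stratification factors are already collected (Sections 5.7, 6.2.1 and 7.0). The statistical price is the power loss shown in the working and more parameters per event. If the four-marker model proves unstable, fitting each marker singly with the clinical covariates keeps the count lower: one marker, arm, log PSA and three factors make 6 parameters, or about 8 events each.

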11.0 STATISTICAL CONSIDERATIONS

11.1 Randomization

Patients will be randomized with equal probability to receive the dietary intervention (experimental arm) or dietary information (control arm). A total of 464 patients will be enrolled to this trial, 232 patients per arm. The study will take a total of 5 years: about 3 years of accrual with an expected accrual rate of 15 patients per month, and 2 years of follow-up for each patient.

Stratification factors: Randomization will be stratified by age (≤ 70 years vs. > 70 years), race (African American vs. Other) and baseline prostate biopsy (0-12 months prior to registration vs. >12 -24 months prior to registration).

11.2 Design

Each patient will be followed for 24 months, and PSA will be evaluated every 3 months starting from baseline. Prostate biopsies are taken at baseline and 24 months.

The primary outcome of interest in this prevention trial is disease progression defined by (a) PSA doubling time (PSADT) < 3 years, (b) PSA ≥ 10 at any time, or (c) Gleason sum on repeat biopsy ≥ 7 for men younger than 70 years and $\geq 4+3 = 7$ for men 70 years or older. These criteria are drawn from one of the largest active surveillance studies to date, the Toronto cohort (12). Data from this cohort indicate that approximately 20% of patients on active surveillance will progress by these criteria: 14% by PSA doubling time and 8%-10% by Gleason score.

Thus, using the log-rank test with a two-sided $\alpha = 5\%$, a sample size of 418 will provide 80% power to detect a difference in progression rate (PGR) of 20% in the control and 10% in the experimental arm during 24 months of follow-up. Under the exponential distributions for the time to progression, the 2-year PGR of 20% vs. 10% corresponds to a hazard ratio (HR) of 2.118. Assuming 10% of dropout rate (including patients who are treated before progression), a total of 464 patients will be enrolled to this trial.

Centralized pathology review will be conducted on the tissue specimens of the first 50 patients. From an analysis of grading by community vs. Johns Hopkins pathologists, Gleason grading of adenocarcinoma in prostate needle biopsy tissue (106), Gleason score was changed from 3+4 by community review to 4+3 by Johns Hopkins review for about 14% of men and from 6 or below to 7 or above for about 8% of men. Assuming about 30% of men in this study will be >70 years old and these two types of changes occur uniformly over the whole range of age, we believe that no more than 10% of men will become ineligible for the study by the centralized pathology review. We will consider increasing the sample size by a maximum of 10% depending on the proportion of men who become ineligible by central pathology review.

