- 4.1.10** For men ≤ 70 years, biopsy Gleason score ≤ 6 ; for men > 70 years, biopsy Gleason score $\leq (3 + 4) = 7$.

4.1.11 Required Initial Laboratory Values:

- Serum PSA < 10 ng/mL

NOTE: Baseline PSA for determination of eligibility must be measured after discontinuation of any 5-alpha reductase inhibitors.

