11.3 Analysis

The proportion of men who become ineligible by central pathology review will be estimated for each arm. The primary analysis will be done using data from eligible subjects, especially using Gleason scores from central review. However, all statistical analyses will be conducted for the data sets from eligible patients only, as well as all patients randomized in the sensitivity analysis.

Progression: PSADT will be calculated as \log_2 divided by the slope (the least squares estimator) of \log (PSA) observations over time using all available PSA measurements, starting from the time point at which we have three PSA measurements (i.e. the first

PSADT of a patient is calculated at month 6 using the PSA measurements collected at months 0, 3 and 6 if there are no missing PSA measurements.” In order to avoid any miscalculation, the PSADT will be calculated at the Alliance Statistics and Data Center, not by each individual site.

Time to progression data will be analyzed using the log-rank test for univariable analysis and the Cox’s proportional hazards regression for multivariable analysis adjusting for the stratification factors and other prognostic factors. For the patients who proceed to treatment with surgery, radiation, local ablative therapy or hormonal therapy before progression within the 2-year follow-up period, the progression time will be censored at the time of withdrawal for treatment.

A recent study in a similar cohort of men undergoing active surveillance (102) reported that PSA kinetics was not closely associated with progression on subsequent surveillance biopsies. In order to address this issue, as a secondary analysis, we will also compare time to progression defined only by Gleason sum on repeat biopsy ≥ 7 for men younger than 70 years and $\geq 4+3 = 7$ for men 70 years or older. Because of decreased number of events, the log-rank test using this definition of time to progression may not have enough power. For example, if the 2-year PGR for the control arm is only 10% by this new definition, then the log-rank test will have only 50% of power with 418 eligible patients with events or full 2 years of follow-up.

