- (3) Time to pathological progression (i.e., Gleason sum on repeat biopsy ≥ 7 for men younger than 70 years and $\geq 4+3 = 7$ for men 70 years or older) will be regressed on PCC in AS patients using Cox’s regression method. Intervention and known predictors including the stratification factors will be adjusted in multivariable analysis.

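### The Gleason progression rule cuts age on the other side of 70 from the entry rule and strata, and the interim looks name PFS while Section 11.3 analyses time to progression

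*Combined protocol and SAP*

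**What the plan says.** **Age cut at entry and in the strata.** Section 4.1.10 requires Gleason 6 or less up to and including age 70 and allows 3+4 above that; the wording is "for men > 70 years, biopsy Gleason score" followed by the higher limit. Section 11.1 says "Randomization will be stratified by age", with the same ≤70 / >70 split as Section 5.7.

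**Age cut in the progression rule.** Section 11.2 counts Gleason 7 or more "for men younger than 70 years and" then requires 4+3 "for men 70 years or older. These criteria are drawn from one of the largest active surveillance studies to date". The list in 8.7.2 uses the same <70 / ≥70 cut and is the only place that fixes when age is taken ("70 years at baseline: Gleason sum"). Section 11.3 repeats the cut twice: in the Gleason-only secondary analysis ("we will also compare time to progression defined only by Gleason sum on repeat biopsy") and in the carotenoid analysis ("Time to pathological progression (i.e., Gleason sum on repeat biopsy").

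**Event at the interim looks.** Section 11.4.1 tests PFS for superiority and futility. The only definition of PFS is in 10.4.4, the biomarker substudy: main-study progression or death. Section 11.3 analyses time to progression, names treatment before progression as a reason for censoring, and does not mention death. Section 8.7.1 lists participant death among the reasons for going off treatment.

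**The concern.** For men over 70 the two rules agree: 3+4 is acceptable at entry, so reaching 3+4 is not progression. For men under 70 they also agree: 3+4 is barred at entry and counts as progression. Only at age 70 do they conflict. Such a man is barred from entry with 3+4, yet may move from 6 to 3+4 without a Gleason event, while the same change in a man of 69 counts. He also sits in the ≤70 stratum, so that stratum holds two Gleason rules; it is one of the covariates in the "multivariable analysis adjusting for the stratification factors and other prognostic factors".

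The PFS label matters because Section 11.4.1 governs looks that can stop the trial. Read literally, a death without progression would be an event there. Section 11.3 leaves open how such a death is handled in time to progression. A data monitoring board should not have to decide this after seeing data.

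**Working it through.** **The plan's own figures first.** From Section 11.2: 20% versus 10% progression at 24 months, exponential times, 80% power, two-sided 5%.

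- HR (experimental/control) = ln(0.9)/ln(0.8) = 0.472; its inverse is 2.118, as stated.
- Freedman's formula gives 62 events; 62/0.15 = 413.3, so about 414 patients, against 418 in the plan.
- 418/0.9 = 464.4, against 464 in the plan.
- Expected primary events: 209 × (0.20 + 0.10) = 62.7.

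**Age cut, side by side.**

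| Age (completed years) | Highest Gleason at entry | 3+4 on repeat biopsy a Gleason event? |
|---|---|---|
| 69 | 6 | yes |
| 70 | 6 | no |
| 71 | 3+4 | no |

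**How many men.** Section 11.2 expects about 30% over 70. The documents do not give the number aged exactly 70. Assume the other 70% are spread evenly over the 21 years from 50 to 70:

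- 464 × 0.70/21 = 15.5 men enrolled; 418 × 0.70/21 = 13.9 eligible.
- If age 70 is twice as common (assumption): 30.9 enrolled, 27.9 eligible.

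**How many events.** The Gleason-only example in 11.3 has 10% in the control arm. At the same HR the experimental arm has 1 − 0.9^0.472 = 4.85%, a mean of 7.43%.

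- 13.9 × 0.0743 = 1.0 event.
- That mean includes men over 70, who face the stricter rule. If their rate were 0% to 4% (assumption), the rate in the rest would be 0.0743/0.70 = 10.6% down to (0.0743 − 0.30 × 0.04)/0.70 = 8.9%. This gives 13.9 × 0.106 = 1.5 down to 13.9 × 0.089 = 1.2 events.
- At double density, 27.9 × 0.106 = 3.0 events.
- Alternative inputs (assumptions): 2% to 8% of men aged 70, and 5% to 10% of controls upgrading to 3+4, half that in the experimental arm. This gives 0.3 to 2.5 events. Power by Schoenfeld's formula moves by at most about 1.5 points from 84.4%.

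Two things pull these figures down: upgrades to 4+3 or higher count anyway, and for the primary endpoint a man with a PSA event is already counted.

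**First interim look.** Section 11.4.1 expects it at about month 33, when 80 men have either progressed or finished follow-up. With 15 men a month from month 6, and time T = 33.5:

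- Entered: 27.5 × 15 = 412.5.
- Progressions: 23.9 control + 11.8 experimental = 35.7.
- Completed without progression: 3.5 × 7.5 × (0.8 + 0.9) = 44.6.
- Sum 80.3, which reproduces the planned look.

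Now let a proportion q of men in each arm die without progression over two years (assumption; the documents give no rate). With d = −ln(1 − q), the PFS hazard ratio is (0.1054 + d)/(0.2231 + d).

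| q | Extra PFS events at the look | HR | Chance of crossing one-sided 0.0025 | Chance of Z < 0 |
|---|---|---|---|---|
| 0 | 0 | 0.472 | 28.6% | 1.2% |
| 1% | 2.2 | 0.495 | 25.9% | 1.5% |
| 2% | 4.4 | 0.516 | 23.6% | 1.8% |
| 3% | 6.6 | 0.536 | 21.6% | 2.2% |

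The last two columns use Z = −ln(HR) × √(events/4). Freedman's version gives about 25% instead of 28.6% in the first row, so read the trend, not the levels. Gleason events come mostly at the 24-month biopsy, so the true event count at this look would be lower than the exponential model gives.

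**The case against.** On age, the conflict needs completed years. The protocol does not say how age is measured, and with exact age almost nobody falls between the two cuts. That stands, and is a reason to state the convention. The rule is the same in both arms, so a reader who infers a biased comparison goes too far. So does one who infers that a man of 70 cannot progress: PSA doubling time and PSA level still apply to him. The silence of 11.2 and 11.3 on when age is taken does not contradict 8.7.2. The mixed stratum has no demonstrated consequence, since the log-rank test is described as univariable and the strata enter only the Cox model. Finally, the progression criteria come from a cited cohort that cannot be checked here, and moving the cut changes the primary endpoint's wording. That is true, but the documents give no reason for treating age 70 differently at entry and at progression.

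On PFS, context points to a loose label. Section 11.4.1 is headed as the primary endpoint, its trigger does not mention death, and the 85% two-year PFS in 10.4.4 is simply the mean of 80% and 90% progression-free. The futility rule only asks for stopping to be considered. A reader might infer that the trial deliberately monitors one endpoint and concludes on another. The documents do not support so clean a contrast: the final one-sided 0.025 stands in the same PFS paragraph. What remains is that one term is defined with death, the other has no rule for death, and the text does not equate them.

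**Conclusion.** Minor, and wrong as written on both counts.

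The age mismatch is a plain inconsistency confined to men aged 70 in completed years. It involves roughly 1 to 3 events under the assumptions shown. This is not a strict bound, because the share of men aged 70 and their upgrade rate are not in the documents.

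The PFS wording has no effect if nobody dies without progressing. With 1% to 3% such deaths in each arm, the hazard ratio at the first look would be about 0.50 to 0.54 instead of 0.472, with a modestly lower chance of stopping for superiority.

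A reader might infer from either point that the sample size is unsound. It is not: 2.118, 418 and 464 are reproduced exactly or to within about 1%, and neither correction changes them.

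**What to change.** Use ≤70 / >70, with age at baseline in completed years, in every Gleason progression definition: 8.7.2, 11.2, and the Gleason-only and carotenoid analyses in 11.3. Changing the progression rule is easier than changing the entry rule and strata, which are applied when men enrol.

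In 11.4.1, replace PFS with the time-to-progression event of 11.3. In 11.3, state that a death without progression is censored at the date of death.

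The cost is a few lines of text, with no new visits, samples or patients. Because the first change touches the primary endpoint definition, it should be made and dated before any comparison of the arms is seen.
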